 13. History of alcohol or substance use disorders (except nicotine and caffeine) meeting DSM-5 criteria within 1-year prior to Screening visit.
 14. Positive alcohol and urine drug screen for opiates, cocaine, barbiturates, tetrahydrocannabinol, methadone, tricyclic antidepressants, benzodiazepines and amphetamine/methamphetamine at Screening or Baseline. Patients with positive testing due to prescribed benzodiazepines, tricyclic antidepressants, barbiturates, or opiates at Screening are accepted but must test negative at Baseline (Visit 2).
 15. Male patients who have pregnant partners.
 16. Female patients who are breastfeeding.
 17. Received an experimental drug or used an experimental medical device within 60 days before the planned start of treatment (Day 1) or have participated in 2 or more clinical trials in the previous 2 years.
 18. QTcF interval at Screening or Baseline greater than 450 msec for males and 470 msec for females.
 19. Patients requiring treatment with drugs likely to prolong QT.

-
20. Patients with known hypersensitivity to MIN-117 or placebo or their excipients (refer to Section 13.1 of the protocol).
 21. Positive hepatitis B surface antigen, or hepatitis C antibody or Human Immunodeficiency Virus (HIV) 1 and 2 antibodies at Screening.
 22. Employees of the investigator or study center, when the employee has direct involvement in the proposed study or other studies under the direction of that investigator or study center; also family members of the employee or the investigator.

Treatments

Patients will be free of any psychotropic medications for a period of 1 week (or 2 weeks for a MAO inhibitor, 4 weeks for fluoxetine) prior to randomization. Eligible patients will be randomized in a 2:1:1 ratio to the following groups:

- Placebo
- 5.0 mg MIN-117
- 2.5 mg MIN-117

Treatments will be administered orally, once a day in the morning for up to 6 weeks.

Efficacy Evaluations

The primary efficacy endpoint will be the change in MADRS total score from Baseline (i.e., the start of double-blind treatment) to the end of the double-blind treatment period (i.e., Week 6). The primary comparisons will be between each MIN-117 dose group (5.0 mg and 2.5 mg) and the placebo group.

Secondary and exploratory efficacy evaluations include the: HAM-A, CGI-S, CGI-I, IDS-SR₃₀, SHAPS, DSST, PSS, ASEX, and sleep parameters as assessed by Somno-Art (at select sites).

Safety Evaluations

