All patients randomized to treatment who receive at least one dose of double-blind study drug will be included in the safety analyses. Summary statistics will be provided for all safety data using appropriate descriptive statistics adverse events, C-SSRS, laboratory tests, ECGs, and vital signs.

TIME AND EVENTS SCHEDULE

Procedures and Evaluations	Screening	Baseline	Double-Blind Phase			Post Study Follow-Up
			3	4	5 / EW ^b	
Visit#^a	1	2	3	4	5 / EW^b	6
Week	-3	1	2	4	6	8
Day	-21 to -1	1	15	29	43	57
Screening/Administrative						
Informed consent	X					
Pharmacogenomic informed consent ^c	X					
Inclusion/exclusion criteria	X	X				
Medical history, SCID-5, MGH-SAFER	X					
Prior medications	X	X				
Preplanned surgery/procedures	X					
Height	X					
Pregnancy test ^d	X	X		X	X	X
Alcohol and Drug Screen	X	X				
TSH, serology	X					
Taper of psychotropic drugs	X ^e	X ^e				
Randomization		X ^f				
Study Drug						
Administer/Dispense study drug		X	X	X	X ^g	
Study drug accountability			X	X	X	
Pharmacokinetics						
Blood sample collection ^h		X	X	X	X	X
Pharmacodynamics						
Blood sample collection		X			X	
Pharmacogenomics						
Blood sample collection		X ⁱ				
Efficacy						
Investigator-Rated: MADRS, HAM-A, CGI-S	X	X	X	X	X	
Investigator-Rated: CGI-I			X	X	X	
Investigator-Rated: DSST		X	X	X	X	
Subject-Rated: SHAPS, A-SEX	X	X	X	X	X	
Subject-Rated: IDS-SR₃₀	X	X			X	
Subject-Rated: PSS		X			X	
Sleep recording (Somno-Art) ^j	X	X			X	
Safety						
Physical examination	X	X			X	X
12-Lead ECG (triplicate) ^k	X	X		X	X	X
Vital signs, temperature, weight ^l	X	X	X	X	X	X
Clinical laboratory tests ^m	X	X			X	X
C-SSRS	X	X	X	X	X	X
Adverse Events	Continuous					
Concomitant therapy	Continuous					

Abbreviations and footnotes on the following page.

Abbreviations: A-SEX = Arizona Sexual Experiences Scale; CGI-I = Clinical Global Impression of Improvement Scale; CGI-S = Clinical Global Impression of Severity Scale; C-SSRS = Columbia Suicide Severity Rating Scale; DSST = digit symbol substitution test; HAM-A = Hamilton anxiety scale; IDS-SR₃₀ = Inventory of Depressive Symptoms - Subject-Rated; MADRS = Montgomery-Asberg Depression Rating Scale; PSS = Perceived Stress Scale; SCID-5 = Structured clinical interview for DSM-5; SHAPS = Snaith-Hamilton Pleasure Scale.

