4.3. Prior and Concomitant Therapy

4.3.1. Prior Therapy

Any medication (including, but not limited to, over-the-counter medicines such as aspirin, antacids, vitamins, mineral supplements, and herbal preparations) that the patient is receiving at the time of Screening, or receives during the study, must be recorded on the appropriate eCRF along with the reason for use, dates of administration, and dosages.

- Women must remain on a highly effective method of birth control (see [Section 4.1, Inclusion Criteria](#)).
- Patients must not use antidepressant within 1 week of the time they will take their first dose of study medication, or MAO inhibitor medications within 2 weeks, or fluoxetine (Prozac) within 4 weeks of the time they will take their first dose of study medication (i.e., 5 half-lives of the antidepressant).
- Patients must not use other prescription medication within 7 days (or per study physician's recommendation) prior to Baseline (Day 1) visit except those allowed in [Attachment 1](#) (Allowed and Prohibited Concomitant Medications). An exception is that women using hormone replacement therapy or hormonal contraception who have been using it continuously for at least 30 days before dosing may take the medication.

Other exceptions justified by the patient's medical condition could be allowed after the Sponsor's Responsible Medical Officer approval (refer to [Section 4.3.2](#)).

- Patients must not use herbal medications (e.g., St. John's Wort, ephedra, ginkgo, ginseng, and kava kava) within 7 days prior to Baseline visit or during the study.

Information on the dose, date of last administration, length of time on medication and reason for stopping or changing the medication will be collected in the source documents and appropriate eCRF pages.

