4.3.2. Concomitant Therapy

All medications except study drug, administered to a patient during the study, should be documented in the eCRF as concomitant medications.

In general, concomitant medications with primary CNS activity, as well as CYP 2C8 and CYP 3A4/5 inhibitors, CYP 2C8 and CYP 3A4/5 inducers, and concomitant medications metabolized through CYP 2C9 are not allowed in this study (refer to [Attachment 1](#)).

As the list of prohibited/allowed concomitant medications ([Attachment 1](#)) is not exhaustive, other concomitant medications justified by the patient's medical condition could be allowed on a case by case basis after Sponsor's Responsible Medical Officer approval.

As a general rule:

- Patients must not use psychotropic drugs other than the study medications at any time during the study. For a complete list of prohibited therapies, please refer to [Attachment 1](#).

-
- Patients must be strongly discouraged from using alcohol or illicit substances during the entire study.
 - Ongoing psychological treatment (eg, Cognitive Behavior Therapy, Interpersonal Psychotherapy, Psychodynamic Psychotherapy, etc.) if it started > 3 months prior to the double-blind treatment phase, if the investigator deems the psychological treatment to continue during the study.

Patients should be discontinued from the study if any prohibited medications are used during the study (the Sponsor's Responsible Medical Officer can allow exceptions).

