9. PATIENT COMPLETION/WITHDRAWAL

9.1. Completion

A patient will be considered to have completed the study if he or she has completed assessments at Week 6 of the double-blind treatment phase. Patients who prematurely discontinue study treatment for any reason before completion of the double-blind treatment phase will not be considered to have completed the study. The investigational drug will not be available after the completion of the study.

9.2. Withdrawal from the Study and Replacement.

The patients have the right to withdraw from the study at any time for any reason, without the need to justify.

A patient will be withdrawn from the study for any of the following reasons:

- Patient withdraws consent.
- Lost to follow-up.
- Termination of the study.
- The investigator believes that for safety reasons (e.g., adverse event) it is in the best interest of the patient to stop treatment.
- The patient becomes pregnant.
- Failure to use an acceptable method of birth control.
- Significant deviation from the protocol.
- Occurrence of a treatment-related serious adverse event.
- Concurrent illness and requirement of a prohibited medication.
- The patient meets one of the following .stopping criteria:
 - Patient with significant increase in ALT [i.e., > 5 upper limit of normal (ULN)].
 - Patient with abnormal laboratory results with simultaneous increases of total bilirubin (> 2 ULN), ALT (> 3 ULN) and alkaline phosphatases (< 1.5 ULN).
 - Patient with sustained mean QTcF (calculated using Fridericia's formula) value > 500 msec (confirmed by a second ECG under strict resting position and at minimum at ½ hour distant from the first measurement).
 - Patient with sustained increase of more than 60 msec in the mean QTcF compared to Baseline (confirmed by a second ECG under strict resting conditions).

If a patient discontinues treatment before the double-blind phase ends, attempts to obtain end-of-treatment and follow-up assessments must be made. In case a patient is lost to

follow-up, every possible effort must be made by the study site personnel to contact the patient and determine the reason for discontinuation/withdrawal. The measures taken to follow-up must be documented. When a patient withdraws before completing the study, the reason for withdrawal is to be documented in the eCRF and in the source document. Study drug assigned to the withdrawn patient may not be assigned to another patient. Patients who withdraw will not be replaced.

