ATTACHMENT 1: ALLOWED/PROHIBITED CONCOMITANT MEDICATIONS

The list is not exhaustive; other concomitant medications could be allowed after Sponsor's Responsible Medical Officer approval – As a general rule, CYP 2C8 and CYP3A4/5 inducers and inhibitors as well as drugs metabolized through CYP2C9 are **always** prohibited.

Drug Class	As Needed	Chronic Use	Comments
Analgesics	Y	N	Non-opiate analgesics only.
Anorexics	N	N	
Antacids	Y	N	
Antianginal Agents	N	N	
Antiarrhythmics	N	N	
Antiasthma Agents	Y	Y	Inhaled agents only.
Antibiotics	Y	N	
Anticholinergics	N	N	
Anticoagulants	N	Y (1)	Aspirin (max. 325 mg/day) is allowed as chronic anti-platelet treatment.
Anticonvulsants	N	N	
Antidepressants	N	N	
Antidiarrheal Preparations	Y	N	
Antifungal Agents:			
Systemic	N	N	
Topical	Y	Y	
Antihistamines	Y	N	Allegra, Claritin, and Zyrtec are allowed.
Antihypertensives	N	Y (1)	Telmisartan, ramipril, atenolol are allowed
Anti-inflammatory Drugs	N	N	
Antinauseants	Y	N	
Antineoplastics	N	N	
Antiobesity	N	N	
Antipsychotics	N	N	
Anxiolytics	N	N	
Cough/Cold Preparations	Y	N	Use of cough and cold preparations containing pseudoephedrine or phenylpropanolamine is not permitted. Decongestants containing narcotics are not permitted.
Diuretics	Y	Y (1)	Amiloride and hydrochlorothiazide are allowed
H2-Blockers	Y	N	
Hormones	N	Y	Only thyroid hormone replacement, oral contraceptives and estrogen replacement therapy are allowed.
Hypoglycemic Agents	N	Y (1)	Metformine is allowed
Hypolipidemics	N	Y (1)	Rosuvastatin is allowed
Insulin	N	N	
Benign Prostatic Hypertrophy	N	Y(1)	Finasteride, dutasteride are allowed
Muscle Relaxants	N	N	
Psychotropic drugs not otherwise specified (including herbal products)	N	N	No drugs with psychomotor effects or with anxiolytic, stimulant, antipsychotic, or sedative properties are allowed.
Sedatives/Hypnotics	N	N	

(1) Allowed for some specific medications. Please contact the Medical Monitor as needed.

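### Exclusion 19 keeps out patients who require drugs likely to prolong QT, but the on-study medication rules have no QT criterion, which leaves a small gap in the classes allowed as needed

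*Protocol*

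**What the plan says.** **At entry.** Criterion 19 excludes "Patients requiring treatment with drugs likely to prolong QT". The wording is the same in the Synopsis and in 4.2. In the Time and Events Schedule, the row "Inclusion/exclusion criteria" is marked only at Screening (Visit 1) and Baseline (Visit 2).

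**In the week before Baseline.** Section 4.3.1 bars other prescription drugs for 7 days "prior to Baseline (Day 1) visit except those allowed in" Attachment 1, so it defers to the same list that applies later.

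**On study.** Section 4.3.2 begins its list of what is not allowed with "In general, concomitant medications with primary CNS activity, as well as CYP 2C8 and CYP 3A4/5 inhibitors, CYP 2C8 and CYP 3A4/5 inducers", and adds drugs metabolised through CYP 2C9. A separate bullet bars other psychotropics and refers to Attachment 1 for the full list. The attachment has its own general rule, "As a general rule, CYP 2C8 and CYP3A4/5 inducers and inhibitors as well as drugs metabolized through CYP2C9 are" always prohibited, followed by a table of drug classes marked Y or N for as-needed and chronic use.

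**Enforcement.** Two clauses attach a consequence to medication use. Section 4.3.2 says "Patients should be discontinued from the study if any prohibited medications are used during the study", subject to medical-officer exceptions. Section 9.2 lists "Concurrent illness and requirement of a prohibited medication" as a reason for withdrawal.

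**Exceptions.** Under 4.3.2, other medications justified by the patient's condition "could be allowed on a case by case basis after Sponsor's Responsible Medical Officer approval".

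**The concern.** Criterion 19 reflects a judgement that MIN-117 should not be combined with drugs likely to prolong QT. That combination can occur only once dosing starts, yet the criterion is checked only up to Day 1 and no later rule takes it over. A site that followed Attachment 1 exactly could give a short course of such a drug, and neither enforcement clause would apply.

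The need for these classes is foreseeable from the sponsor's own data (Protocol 1.4.2). In the Phase 2a study, nausea was the most common treatment-emergent event (9.8%, 8 patients across all arms, paroxetine included), and infections and infestations affected 11.0%. What is at stake is a patient-safety safeguard that is not carried forward. The efficacy comparison is not involved.

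**Working it through.** This is a comparison of texts. No figure in the plan has to be reproduced.

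**Step 1: does any on-study rule use QT as a criterion?**

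- 4.3.2, not-allowed sentence: CNS activity and CYP pathway; no QT.
- 4.3.2, psychotropic bullet: drug class; no QT.
- Attachment 1, general rule: CYP pathway; no QT.
- Attachment 1, 33 class rows with comments: class, route, named drugs, or psychomotor and sedative properties; no QT.
- Medical-officer exception, stated once in 4.3.1, twice in 4.3.2 and once in Attachment 1: none of the four carries a QT condition.

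**Step 2: which classes does Attachment 1 leave open?** Counting rows, with systemic and topical antifungals separate:

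- not allowed as needed or chronically: 16
- chronic use only: 6
- allowed as needed: 11
- total: 16 + 6 + 11 = 33

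Of the 11 as-needed rows, 5 carry a limiting comment (analgesics, antiasthma agents, antihistamines, cough/cold preparations, diuretics) and 1 is limited by route (topical antifungals). That leaves 11 − 5 − 1 = 5: antacids, antibiotics, antidiarrheals, antinauseants and H2-blockers. All five are marked N for chronic use.

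**Step 3: what else narrows those five rows?** The CYP 2C8, 3A4/5 and 2C9 bars, the primary-CNS-activity bar and the bar on psychomotor, anxiolytic, stimulant, antipsychotic or sedative properties still apply within them. Anticholinergics, antiarrhythmics and systemic antifungals are closed as classes. A QT-prolonging drug caught by one of these rules is prohibited, but on other grounds. The documents do not say whether any remains.

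**Step 4: would enforcement reach a drug that remains?** Both medication clauses depend on the drug being prohibited. A drug in a Y class that meets no other bar is not, and the exception route is worded for medications other than those listed.

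**Step 5: what other controls exist?**

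- The investigator may withdraw a patient for safety reasons (9.2).
- Patients are withdrawn for a confirmed, sustained mean QTcF above 500 msec or a sustained rise above 60 msec from Baseline (9.2).
- Triplicate ECGs are scheduled at Screening, Baseline and Visits 4, 5 and 6. None is scheduled at Visit 3, so the first scheduled on-treatment ECG is at Day 29. Steady state is estimated after 10 days (1.4.1), which leaves about 29 − 10 = 19 days at steady state before it.
- Concomitant medications and ECGs are listed by patient (SAP 5.4.3 and 5.4.4).

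**The case against.** The strongest reply is that criterion 19 describes a patient's need and is not a ban on drugs. Excluding people who require QT-prolonging treatment, while managing brief incidental use through class rules and ECGs, is a coherent design. Drug use in the week before Baseline is already governed by Attachment 1, so the list does not change on Day 1. This much stands: a reader might infer that the protocol bans these drugs and then permits them, and the text does not support that. What remains is narrower. The patient-level screen is not repeated, and nothing based on QT replaces it.

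It can also be said that the list is expressly not exhaustive, that the rule in 4.3.2 is qualified as general, and that 9.2 allows withdrawal for safety or for a significant protocol deviation. These are partial safeguards. Safety withdrawal is discretionary, and a site complying with Attachment 1 is not clearly deviating from the protocol. The stopping rules act only after the interval has lengthened.

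A third point is cost. Making these drugs prohibited brings in the discontinuation sentence of 4.3.2, so a short course could lose a randomised patient and the Week 6 MADRS. Early discontinuation is the intercurrent event of the primary estimand (SAP 5.2.1). This stands, and the fix has to deal with it.

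**Conclusion.** The concern holds in this limited form. The on-study rules contain no QT criterion, so short-term use of a QT-prolonging drug from a class allowed as needed is not prohibited after Day 1 unless another rule bars it. That any such drug passes the other bars is an assumption. The documents give no frequency for such prescriptions, and none is estimated here. At most 162 of the 324 planned patients (2 × 81) receive MIN-117. The gap is small and unquantified, and closing it is a cheap improvement.

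Three stronger readings are not supported:

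- **A known hazard.** MIN-117 blocks hERG in vitro (IC50 0.43×10⁻⁶ mol/L). However, action potential duration lengthened only 5% at the highest concentration tested (3×10⁻⁵ mol/L), and conscious monkeys showed no QT or QTc effect up to 100 mg/kg (Protocol 1.3.2). In the 14-day study, mean QTcB changes at 3 and 7.5 mg were mainly positive. They were judged not clinically relevant and possibly explained by heart rate, and no value exceeded 480 msec.
- **An exposure rate.** The count of five open rows describes the list. It says nothing about how many QT-prolonging drugs are permitted or how often they would be used.
- **A threat to the results.** Nothing here affects the MADRS or HAM-A comparisons.

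**What to change.** Make three short edits to the protocol:

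1. In 4.3.2, add drugs likely to prolong QT to the sentence listing what is not allowed.
2. In Attachment 1, directly after the CYP rule and outside its always-prohibited wording, add: *Drugs likely to prolong QT are not allowed in any class, including classes marked Y, unless approved by the Responsible Medical Officer after a documented QT review.*
3. In 4.3.2, state that a short course already taken is referred to the medical officer, who may allow the patient to continue, and does not cause automatic discontinuation.

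No row-by-row comments are needed, because the second edit covers every class. The SAP can stay as it is, since the relevant listings already exist.

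The cost is slightly narrower as-needed choices, a few more medical-monitor calls and a small risk of extra discontinuations, which the exception route and the third edit limit. The phrase 'likely to prolong QT' would stay undefined, as it is in criterion 19 now, so sites would rely on the medical officer in doubtful cases.

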1. INTRODUCTION

1.1. Background on the Disease

Major depressive disorder (MDD) is a common, serious, recurrent disorder, with worldwide lifetime prevalence estimates ranging from 1% in the Czech Republic to 17% in the United States (US). Its negative impact on role functioning in various settings (e.g., school performance, marriage, parenting, and the workplace), quality of life, physical health, and life expectancy has been well-documented. Loss of work production and absenteeism due to major depressive episodes or MDD has been estimated to account for approximately 30 to 50 billion dollars in annual human capital (Kessler 2013). In fact, as of October 2015, and with an estimated 350 million sufferers, depression has been ranked by the World Health Organization as the leading cause of disability worldwide, and the prevalence is rising (WHO 2015). MDD is associated with significant comorbid medical conditions which include diabetes, hypertension, and cardiovascular disease, and there is an increased risk of early mortality in patients with MDD (Kessler 2013).

While existing therapies for this disease are available, their effectiveness is limited due to unacceptable side effects, different levels of efficacy for individual subjects requiring a physician to test, check, and alter (or change) therapies during treatment, and subject adherence due to the need for multiple daily doses (Rush 2006).

The use of antidepressants for the treatment of MDD is well established. However, effect sizes of currently available antidepressants are rather small than medium (Kirsch 2008; Turner 2008). Most subjects with major depression are best treated with a combination of antidepressants and psychotherapy. It is generally 1 to 4 weeks before antidepressants take effect. This delayed clinical response to the antidepressant makes it difficult to establish the optimal dose quickly, which is of paramount importance for the treatment of a clinically depressed subject. The individual dose is usually decided by trial and error, with the subject's previous response being the most useful guide (Spigset 1999).

1.2. MIN-117 Pharmacological Profile and Rationale as a Unique Antidepressant

MIN-117 is an investigational antidepressant belonging to a new chemical class, the benzofuran derivatives. The chemical designation is (2*S*)-1-[4-(3,4-Dichlorophenyl)piperidin-1-yl]-3-[2-(5-methyl-1,3,4-oxadiazol-2-yl)benzo[*b*]furan-4-yloxy]propan-2-ol monohydrochloride. MIN-117 is characterized by its affinity for 5-HT_{1A} pre-synaptic autoreceptors and 5-hydroxytryptamine transporters (5-HTT). The K_i values for 5-HT_{1A} receptors and 5-HTT of human were 5.0 and 0.81 nmol/L, respectively. MIN-117 acts as a serotonin reuptake inhibitor. In addition, MIN-117 has high affinity for adrenergic alpha (α)₁ and serotonergic 5-HT_{2A} and acts as antagonist to each receptor. MIN-117 is also active as a dopamine transport (DAT), by inhibiting reuptake of dopamine from the synaptic cleft. Furthermore, MIN-117 has moderate affinity for 5-HT_{2C} and also acts as a moderate norepinephrine transporter (NET) inhibitor.

For the most accurate and current information regarding the efficacy and safety of MIN-117, refer to the latest version of the Investigator's Brochure for MIN-117.

